11.4.2 Analysis of Secondary Endpoints

A secondary aim of the study is to compare participants' engagement with the mobile app between the three incentive conditions. The primary measure of this endpoint is the number of sessions completed over the course of treatment. Secondary measures are the total time spent engaging with the app during the course of treatment and participants' impressions of the program as assessed by the Mobile Application Rating Scale (uMARS). The uMARS is a 26-item measure of mobile application engagement, functionality, aesthetics, quality of information, and perceived impact. Higher scores indicate greater application feasibility and lower scores indicate poorer application feasibility.

11.5 Interim Analysis

No planned interim analysis.

11.6 Reporting and Exclusions

Not applicable as we will not be using a drug or medical device.

12. Adverse Event Reporting Requirements

Adverse event (AE) monitoring and reporting is a routine part of every clinical trial. The investigator will be required to provide appropriate information concerning any findings that suggest significant hazards, contraindications, side effects, or precautions pertinent to the safe use of the drug or device under investigation. Safety will be monitored by evaluation of adverse events reported by patients or observed by investigators or research staff, as well as by other investigations such as clinical laboratory tests, x-rays, electrocardiographs, etc.

12.1 Adverse Event Definition

An adverse event (also referred to as an adverse experience) can be any unfavorable and unintended sign (e.g., an abnormal laboratory finding), symptom, or disease temporally associated with the use of a drug, and does not imply any judgment about causality. An adverse event can arise with any use of the drug (e.g., off-label use, use in combination with another drug) and with any route of administration, formulation, or dose, including an overdose.

12.1.1 Investigational Agent or Device Risks

Participants will be asked to engage with the mobile application at least 4 days a week for 20-25 minutes per session. These sessions can be done at the participants' convenience for various lengths of time. The only potential risk is that the tasks can be boring or frustrating for some people, but participants are allowed to take breaks, or to make sessions shorter. Participants may also decide to stop participating at any time.

12.1.2 Adverse Event Characteristics and Related Attributions

There will be no adverse events during this study as a result of the mobile CBT program, as patients will be continuing regular anxiety treatments.

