WCM	Weill Cornell Medicine

Protocol Summary

Please provide a brief protocol summary.

Full Title:	Mobile Cognitive Behavior Therapy Targeting Anxiety Disorders
Short Title:	Mobile CBT in Anxiety
Clinical Phase:	N/A – no drug or device involved
Principal Investigator:	[name]
Sample Size:	N = 120
Accrual Ceiling:	We plan to screen up to 300 subjects.
Study Population:	18-25 year olds who have been diagnosed with an anxiety disorder as per the Anxiety Disorders Interview Schedule.
Accrual Period:	We anticipate complete accrual of participants taking up to 1 year
Study Design:	Participants in this study will use an online Cognitive Behavior Therapy program to assist with treatment of their anxiety symptoms. This program is being developed by Weill Cornell Medicine faculty as part of the University of Pennsylvania Center for Health Incentives and Behavioral Economics's established online platform called "Way to Health." All participants in the study will be using the program; as this is a pilot study testing the feasibility of using an online CBT program plus non-monetary incentives. Participants will be told to use the program for at least 20 minutes per day, 2 days per week, for up to 6 weeks. Participants will check in once a week in person or over the phone or a HIPAA-compliant virtual meeting platform. There will also be one follow up visit 6 weeks after they have stopped using the program.
Study Duration:	3 months
Study Agent/	
Intervention Description:	There is no drug or invasive device being used; rather, we are simply providing an online Cognitive Behavior Therapy program through an existing online platform called "Way to Health"
Primary Objective:	The primary objective is to examine different ways of motivating people to make use of the online therapy program, and to assess whether social supports are as efficacious, or more efficacious, than a reward mechanism such as non-monetary incentives. We will randomize subjects to one of three conditions: a social support condition, a gain-framed condition in which participants can earn "points" for completing their assigned sessions, and a

loss-framed condition in which participants lose “points” for failing to complete their assigned sessions on time. We will compare change in anxiety from baseline to end of treatment between these three conditions.

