2.4 Risk/Benefit Assessment

Since this is a pilot study, and we are only trying to determine the feasibility of a mobile CBT program, subjects will not be using the CBT program in place of existing therapies. All existing therapeutic programs that subjects are part of will continue as normal. Thus, this study presents very minimal risk to participants. They may find the mobile CBT program boring or uninteresting, but since it is based in CBT theory, it will not make anxiety symptoms worse.

The optional MRI scan also presents minimal risk to participants. There will be no contrast used. There are no known side effects of an MRI scan. Risks include the potential for discomfort from MRI scanning. Some people (about one in ten) feel claustrophobic (fear closed spaces). Participants will be able to squeeze an emergency ball to communicate that they want to end the scan at any time.

Risks related to the EEG recording are also minimal. Participants may complete a computer task during the EEG that includes unpleasant (death, mutilation) and erotic images. These images are drawn from a widely used stimulus set (The International Affective Picture System (IAPS)) that has been used in many prior EEG studies, including [name] study with suicidal patients at WCM (protocol # 1603017115) as well as numerous studies outside of WCM (e.g. Albanese, 2019; Schupp, 2004; Weinberg, 2010; Sabatinelli, 2013). Risks include possible distress related to looking at emotional pictures or thinking about emotional situations; possible fatigue or boredom as a result of performing similar actions repeatedly; and possible mild skin irritation (redness) where the sensors contact the participant's scalp. Skin irritation in response to EEG recording is rare and temporary. Participants are offered breaks between the tasks and can choose to discontinue the EEG recording at any time.

In addition, the potential benefit of this study is that a mobile CBT program is created and is deemed feasible in this population. This is a potentially huge benefit, as mobile CBT programs could serve to enhance current CBT practices in patients with an anxiety disorder.

3. Subject Selection

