3.3 Exclusion Criteria

Individuals who do not meet the cutoff score on the ADIS or who have a primary diagnosis other than an anxiety disorder will be excluded from participating in this study. Additionally, participants who are currently in cognitive behavioral therapy outside of the app or who have changed their dose of a psychiatric medication in the past 12 weeks will be excluded. Participants with the intent or plan to attempt suicide will be excluded from this study and provided referrals for treatment.

4. Registration Procedures

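### The adverse event definition in Section 12.1 depends on use of a drug in a trial that gives none, and Section 12.1.2 rules out program-related events in advance, contradicting the DSMP

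*Combined protocol and SAP*

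**What the plan says.** All references are to the combined protocol and SAP.

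- **Definition (12.1).** An adverse event is an unfavorable, unintended sign, symptom or disease "temporally associated with the use of a drug", with no judgment about cause implied. The next sentence begins "An adverse event can arise with any use of the drug" and goes on to off-label use, drug combinations, route, formulation, dose and overdose.
- **Intervention.** The Protocol Summary, under the intervention description, states: "There is no drug or invasive device being used". Section 11.6 reads: "Not applicable as we will not be using a drug or medical device".
- **Attribution (12.1.2).** The whole section is one sentence. It opens "There will be no adverse events during this study as a result of the mobile CBT program" and gives as its reason "as patients will be continuing regular anxiety treatments".
- **DSMP (13).** The only adverse events it foresees leading participants to stop treatment are tiring of, or being bored by, the app tasks. All adverse events are to go to the monitoring board as they occur.
- **Other safety text.** Section 10.1 has REDCap capture adverse event data for everyone enrolled. Section 12 bases monitoring on what patients report and what staff observe. Section 12.2.4 has events followed until they resolve or stabilize.

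**The concern.** A safety section has to say which occurrences count as adverse events and how their relation to the intervention is judged. Here the first rule refers to something the trial does not give, and the second is replaced by a conclusion reached before any data exist.

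What is at stake is the meaning of one possible safety statement. Section 11 says the pilot data will support an NIH grant application. If that application were to say that no adverse event was related to the program, a reader could not tell whether this was observed or followed from the protocol's wording.

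**Working it through.** No arithmetic applies beyond a word count, and the plan gives no figure to reproduce. The check sets the sections side by side.

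**1. Does the definition fit the trial?** Section 12.1 uses the word drug 3 times and does not mention the app, the program, MRI or EEG. The Protocol Summary and Section 11.6 say no drug is used. No other section supplies a definition. The criterion in 12.1 is one of timing, and it refers to a drug in general, so an event in someone taking outside medication can satisfy it. An event in someone taking none cannot.

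**2. Does the reason in 12.1.2 hold?** It assumes that participants are in ongoing treatment.

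- Sections 3.2 and 3.3 contain no requirement to be in treatment.
- Section 2.4 says "All existing therapeutic programs that subjects are part of will continue as normal", which covers only those who already have such a program.
- Section 5.3 says only that participants are likely to be seeking outside services.
- Section 3.3 excludes "participants who are currently in cognitive behavioral therapy outside of the app", so one common treatment for anxiety is ruled out at entry.

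Even if every participant were in treatment, that would not show that the app causes nothing. Section 2.2 describes exposure tasks that become more challenging. Distress from such a task is possible whatever other care the participant receives, although the documents give no rate for it.

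**3. Does 12.1.2 agree with Section 13?** Section 13 names tiredness and boredom arising from the app tasks and calls them adverse events. These would result from the program, and 12.1.2 says there will be none that do. Both statements cannot stand.

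**4. What follows if the text is applied as written?**

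| Occurrence | 12.1 | 12.1.2 | 13 |
|---|---|---|---|
| Tired by app tasks, taking no medication | Outside the definition | Cannot be program-related | Foreseeable adverse event |
| Tired by app tasks, taking outside medication | Can fit by timing | Cannot be program-related | Foreseeable adverse event |
| Skin irritation from EEG, taking no medication | Outside the definition | Silent (covers the program only) | Not named |

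The first two rows show the conflict with the DSMP. The first and third show the gap in the definition. In no row can an event be classed as related to the program.

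**The case against.** The strongest reply is that this is template text with little practical effect. Section 12.1 reads like unedited drug-trial wording, and nearby sections still carry template prompts. Sections 2.2 and 12.1.1 put the program under agent-or-device headings, so staff would probably read drug as meaning the program. This lowers the likely consequence. It does not remove the fault, because 12.1 is the operative definition and nothing replaces it. Section 12.1.2 names the mobile CBT program, so it was written for this study. It is phrased as a certainty, not as an expectation of low risk.

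A second reply is that the contradiction rests on mild events, and that boredom is doubtfully a sign, symptom or disease even under a corrected definition. That is fair as to weight. But it is the DSMP that calls these adverse events, so the two sections still disagree.

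Three stronger readings are tempting, and the documents do not support them:

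- *That none of the risks the protocol names could count as an adverse event.* Section 12.1 sets a temporal criterion, not a causal one, and does not limit it to a study drug. Outside medication is expected (5.3) and tracked at all eight visits (5.1.2), so some events could fit.
- *That the MRI and EEG risks in Section 2.4 also contradict 12.1.2.* That sentence covers only the mobile CBT program. For MRI and EEG the problem is the definition alone.
- *That safety is not monitored.* Sections 10.1, 12, 12.2.4 and 13 provide for capture, monitoring, follow-up and board reporting, and none of these depends on relatedness. The GAD-7 and PHQ-9 are also given at every visit from baseline to follow-up, so worsening symptoms would show in the data.

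**Conclusion.** Wrong as written; minor. The definition in 12.1 does not fit a trial without a drug. The statement in 12.1.2 settles attribution in advance, on a reason that does not support it and against the DSMP.

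The size is limited to how events are defined and attributed. Followed literally, 12.1.2 makes the count of program-related events zero by wording. How many events this would touch cannot be computed from the documents. The efficacy and engagement comparisons between the three incentive conditions are not affected.

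The conclusion assumes that 12.1 and 12.1.2 are applied as written. If staff read drug as the program and judge relatedness anyway, the practical effect shrinks to an inconsistency in the protocol text.

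**What to change.** - **Section 12.1:** replace the reference to use of a drug with *participation in the study (app use including exposure tasks, optional MRI, optional EEG)*, and remove the second sentence, which applies only to drugs.
- **Section 12.1.2:** delete the sentence and state that the investigator judges the relatedness of each event individually.

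Section 13 can then stand as it is. The cost is new wording in two short sections and one relatedness judgment per event, with no added visits, scales or analyses. The sponsor gives up only the assurance that program-related events cannot occur, which no data yet support.

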12.2.3 Reporting of SAE to Insert Pharmaceutical Company Name

N/A

12.2.4 AE/SAE Follow Up

Please specify any follow up procedures for any AEs/SAEs that occur on study. Sample language is provided below in *italics*.

All SAEs and AEs reported during this study will be followed until resolution or until the investigator confirms that the AE/SAE has stabilized and no more follow-up is required. This requirement indicates that follow-up may be required for some events after the patient discontinues participation from the study.

13. Data and Safety Monitoring Plan (DSMP)

- We will be using REDCap, a secure web application, to manage participant data. Only individuals listed as co-investigators on the protocol will have access to this database.
- All data that is collected by the study team will be stored in the REDCap database. All questionnaire data collected for the study (see attachment) will be stored in the REDCap system.
- Participants can discontinue engagement in the study at their own discretion. The only foreseeable adverse events that may cause subjects to terminate protocol treatment is that they may get tired or bored of the tasks they asked to engage in on the mobile application.
- The researchers will report all adverse events and unanticipated problems to the monitoring board as soon as they occur.
- The monitoring entity will review data/events annually with the continuing review for the study.
- The researchers will terminate the protocol if they receive information from the monitoring board that they should do so.
- The monitoring entity's comments/reviews will be disseminated during the continuing review.
- The study application (CBT App) environment is stored and processed on the Weill Cornell ITS server with analytics information sent to Heap Analytics, and text message communications via Way to Health. Data on IP address, phone carrier, and city, as well as use of the app is collected on these platforms.

These are companies outside of Weill Cornell that will have access to participants' personal information. If these data are further disclosed by them or their business partners, it may no longer be covered under the privacy protections. Text messaging does not provide a completely secure and confidential means of communication. Participants are made aware of the risks that are inherent in using text messaging.

References

Please provide the citations for all publications referenced in the text.

